## Health Coaching to Improve Self-Management in Thoracic Transplant Candidates NCT03150095 7/22/2020

PI: [name] MD, Mayo Clinic Rochester, MN

Hypothesis: Individualized health coaching including strategies to address poor resilience, coping with uncertainty, frailty, and/or negative affect will be an effective therapeutic strategy at improving self-management while in the pre-transplant state.

Aims, purpose, or objectives: We will conduct a randomized, controlled pilot trial to test whether heart and lung transplant candidates who receive health coaching will experience improvement in self-management abilities compared to transplant candidates who receive standard pre-transplant care. We will also explore the relationship between self-management and pre-transplant risk factors such as uncertainty, resilience, frailty, and affect.

Background: The ability to adhere to complex medical regimens is critical to achieving successful transplant outcomes, as non-adherent patients may experience graft failure or death following transplantation. Since potential recipients exceed organ availability, identification of candidates who will adhere to complex posttransplant regimens is critically important and emphasized by practice guidelines. When selecting candidates for transplant, physicians attempt to subjectively predict post-transplant adherence because tools that reliably predict future adherence are lacking. Despite rigorous screening procedures pre-transplant, non-adherence is common following transplant. As a result, new strategies for predicting future non-adherence are necessary. Self-management ability, defined as "taking responsibility for one's own behavior and well-being" involves the patient's ability to manage their medical condition, their emotions, and their social roles. Self-management ability can be measured objectively, and it may be improved through interventions such as health coaching. Understanding self-management and related factors such as uncertainty, resilience, frailty, and affect may lead to an intervention for optimizing pre-transplant risk factors and adherence post-transplant.

#### **Study Design and Methods**

This is a randomized, controlled pilot study to be conducted at Mayo Clinic in Rochester, MN examining the effects of a health coaching intervention on the self-management ability of patients awaiting heart or lung transplant. The relationship between self-management and pre-transplant risk factors such as uncertainty, resilience, frailty, and affect will also be explored. Patients on the active or deferred waiting lists or with a waiting list status of "temporarily inactive" will be approached for recruitment in the Transplant Clinic at a routine clinical follow-up appointment (occurring every 1 to 3 months) or by phone or mail. All participants will complete a written consent form in person via email-PTRAX, phone or by mail. After consenting, patients will schedule a research visit to complete baseline measures including questionnaires, a hand grip strength test, a timed gait speed test over a distance of 15 feet, Short Physical Performance Battery (SPPB) and a 60-second body composition scan. A body composition analyzer (InBody 770) will be used to determine body composition (body mass, fat mass, and fat-free mass) via electrical impedance. Participants will also receive an activity monitor at their baseline visit to be worn for 5-7 days. In addition; participants will be given a pedometer to track their steps throughout the study. If participants are unable to schedule a research visit, they may be mailed the questionnaires or sent via Redcap (electronically) and activity monitor will be sent via the mail, which will be returned in postage-paid envelopes. Participants will be randomized to one of two groups while completing their baseline measures. Participants in one group will continue to receive the standard pre-transplant care for 12 weeks. Participants in the intervention group will receive a health coaching intervention in which they will be assigned a health coach trained in motivational interviewing who will call the patient weekly for 12 sessions for an approximately 30 minute intervention. Participants who miss a call will be allowed a make-up call with the goal of finishing 12 calls over a 16-week period. The health coaching calls will be recorded and externally monitored by an independent expert to assure treatment fidelity, and all recordings will remain private. In

addition to the health coaching intervention, participants in the intervention group will also continue to receive standard pre-transplant care. After completion of the intervention, all participants will be asked to complete a follow-up research visit in which they will complete the questionnaires, hand grip strength test, timed gait speed test, SPPB, and bioelectrical impedance test a second time. All participants will also be asked to wear an activity monitor again for 5-7 days. At the end of the intervention, participants will be completed within 90 days of completing the study. Demographic data will be collected at the time of the initial questionnaires and verified with the follow-up questionnaires. If a participant leaves large sections or multiple pages of the questions or indicate that the questions were purposely left unanswered. Psychometric surveys will be stored in a locked cabinet. Data will be entered into a secure password-protected REDCap database. Questionnaire data, measurements, and abstracted data (age, type of transplant, 6 minute walking distance, race, ethnicity, psychological assessment information, marital status, height, weight, date of listing, primary diagnosis, etc.) will be kept in a password-protected REDCap database on our secure network.

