## Study Measures:

Participants will complete the following testing, SPPB measures, and wear an Actigraph at baseline and after completing the intervention (or in an equivalent time-frame if a control patient).

1. Hand grip strength test: Hand grip strength will be measured using a Jamar Digital Hand Held Dynamometer. Participants will complete the grip strength test 3 times with their dominant hand. The 3 trials will be averaged and adjusted by sex and BMI using a normative table.

2. Gait speed test: The participant's gait speed will be measured using a stopwatch as the participant walks a distance of 15 feet at a self-selected walking speed. The average of 3 trials will be calculated and adjusted for sex and height. To determine the participant's SPPB score, the results of the gait speed test will be prorated for 4 meters (13.1 feet). The best of 3 trials will be used to calculate the participant's SPPB score.

3. Short physical performance battery (SPPB): The SPPB consists of a gait speed test over 4 meters (13.1 feet), timed repeated chair stands, and 3 balance tests.

a. Gait speed test: See #2.

b. Timed repeated chair stands: Participants will be asked if they feel safe to stand from a chair without the use of their arms and without assistance. If the participant feels safe to stand from a chair without the use of their arms and without assistance, they will be asked to complete 5 repeated chair stands. The participant's SPPB score will be determined by the time required to complete 5 repeated chair stands.

c. Balance testing: The participant's balance will be tested in side-by-side, semi-tandem, and tandem stands. In the side-by-side stand, participants will stand with their feet as close together as possible. In the semi-tandem stands, participants will stand with one heel touching the big toe of the opposite foot. In the tandem stands, participants will stand with the heel of one foot in front of the toes of the other foot (as if on a balance beam). Participants will be asked to hold each position for up to 10 seconds.

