4. Body composition scan: Participants will stand on the InBody 770 body composition analyzer, which determines body composition by electrical impedance (i.e., sending an electrical signal through the body). Height, weight, BMI, skeletal muscle mass, percent body fat, and segmental lean mass will be recorded. Participants with a pacemaker, an implantable cardioverter-defibrillator (ICD), or an automated ICD (AICD) will not be able to complete this body composition scan. Those patients will have their height and weight collected. BMI will be calculated.

5. Activity monitoring: Participants will receive an Actigraph activity monitor to be worn on the wrist for 5-7 days. The activity monitors are capable of measuring the number of steps taken, the number of calories

burned, the intensity of physical activity, the amount of sedentary time, and other variables. Participants will receive a prepaid addressed envelope to return the activity monitor.

6. Center for Epidemiologic Studies Depression Scale (CES-D): Participants will answer 2 questions from the CES-D about their level of exhaustion.

7. Self-reported weight loss: Patients will be asked whether they intentionally lost 10 or more pounds within the last year. As available, weight changes in kg will also be abstracted from the medical record to trend the weight over the prior year's time.

8. Demographic information: Patients will be asked to self-report their sex, race, ethnicity, marital status, education level, and the relationship of their primary caregiver post-transplant.

9. Questionnaires:
Chronic Respiratory Questionnaire (lung disease only)
Kansas City Cardiomyopathy Questionnaire (heart disease only)
Mishel Uncertainty of Illness Questionnaire
Positive Affect Negative Affect Questionnaire (affect)
Perceived Stress Scale (stress)
PHQ 2 and GAD 2 (mood/affect)
RISC-10 (resilience)
Frailty Deficit Index (frailty)
SMAQ (adherence)
SMAS-30 (self-management)

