Health Coaching to Improve Self-Management in Thoracic Transplant Candidates NCT03150095 5/09/2017

PI: [name] MD, Mayo Clinic Rochester, MN

ANALYSIS PLAN: Sample size: This is a pilot and feasibility study. However, to inform our enrollment we have made the following calculations. Change in SMAS-30. A sample size of 25 in each group will have 80% power to detect an effect size of 0.81 using a two-group t-test with a 0.05 two-sided significance level, where effect size is the end of study difference in means between the two groups relative to the SD of the end of study measures, after adjusting for baseline and other factors. From the literature, we estimate an unadjusted end of study SD for SMAS-30 of 8.5. Whereas we do expect our intervention to impact SMAS-30, it is our clinical impression that without intervention, patients tend to exhibit similar patterns over time. Therefore, we expect the between-person variability in SMAS-30 to be at least as large as the variability in assessing SMAS-30 for the same person at different time points. If these two sources of variability were the same then they would both have a SD of 6.0, in particular the end of study SD for SMAS-30 would be 6.0 or less. With this SD, we would have power to detect a difference of 0.81x6.0=4.9. Thus, this pilot study is reasonably powered. Allowing for a 20% withdrawal rate (primarily due to transplantation during intervention), we will aim for a sample size of 30 per arm. Analysis plan: Demographic characteristics will be summarized by mean, median, SD and range (continuous variables) and counts and percents (categorical variables). Our primary variable will be end of study SMAS-30 (adjusting for baseline), which we will analyze using analysis of covariance (ANCOVA), estimating between group differences. Subgroup analysis will be performed by sex, ethnicity, and race as feasible. A similar procedure to that described above will be employed to impute data if necessary. Missing data and end of study SDs for SMAS-30, adjusting for baseline, will guide analysis and power calculations for future R01 studies. Secondary Outcomes will examine between group differences of changes in gait speed, activity levels, body composition, weights, and RISC-10, PANAS, MUIS, FDI, SMAO, and KCCO or CRO measures to inform future R01 planning. A two-tailed p< 0.05 will be considered statistically significant.

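### Comparing changes drops participants with a remote baseline but an in-person follow-up, and the SAP does not say that body-composition results cover only candidates without an implanted device

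*Protocol*

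**What the plan says.** **Baseline.** Under Study Design and Methods, the protocol places the physical measures at a visit: "patients will schedule a research visit to complete baseline measures including questionnaires, a hand grip strength test, a timed gait speed test". The SPPB and the body scan belong to the same visit. It then opens a remote route: "If participants are unable to schedule a research visit, they may be mailed the questionnaires or sent via Redcap (electronically". These participants also receive the activity monitor by post. No remote version of the gait test or scan is described, and no later baseline test. Randomisation takes place while baseline measures are being completed.

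**Follow-up.** The same section says that "all participants will be asked to complete a follow-up research visit in which they will complete the questionnaires, hand grip strength test, timed gait speed". It lists the other physical measures for that visit too. Study Measures opens in the same spirit: "Participants will complete the following testing, SPPB measures, and wear an Actigraph at baseline and after completing the intervention".

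**Devices.** Study Measures, item 4, says that participants with a pacemaker, ICD or AICD "will not be able to complete this body composition scan". Their height and weight are taken and BMI is calculated.

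**Analysis.** The SAP says: "Secondary Outcomes will examine between group differences of changes in gait speed, activity levels, body composition, weights". It then lists the questionnaires. Its primary variable, end-of-study SMAS-30, is instead analysed by ANCOVA adjusting for baseline. Its one sentence on missing values says that a procedure similar to one described earlier "will be employed to impute data if necessary". No such procedure appears in the SAP.

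**The concern.** The protocol creates two groups whose values are missing by design, and the SAP has a rule for neither.

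The first group has a remote baseline. A change needs two measurements. Someone who enters remotely and later attends follow-up has a real, randomised outcome that a comparison of changes cannot use.

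The second group carries an implanted device. Their fat and muscle mass are never observed at either visit. Any imputed value would have to be borrowed from participants without a device, and the trial data could not check it.

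The SAP says that the secondary outcomes are meant to inform a larger trial. For that purpose the number scorable per arm, and the population behind each SD, are among the main products of the pilot.

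**Working it through.** **Step 1. Who can be scored, reading the sections together.**

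| Participant | Gait: baseline / follow-up | Gait change | Scan change |
|---|---|---|---|
| In person twice, no device | yes / yes | scorable | scorable |
| In person twice, device | yes / yes | scorable | never scanned |
| Remote baseline, in-person follow-up, no device | no / yes | not defined | not defined, though a follow-up scan exists |
| Remote baseline, in-person follow-up, device | no / yes | not defined | never scanned |
| Not seen in person at follow-up | – / no | not defined | not defined |

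Rows 3 and 4 hold follow-up gait values that a change analysis discards. Row 3 also holds usable follow-up scans. Rows 2 and 4 cannot contribute to scan outcomes under any analysis.

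**Step 2. The SAP's own figure.** Inputs: two-group t-test, two-sided 0.05, effect size 0.81, 80% power (SAP, sample size). The detectable effect d solves P(|T| > t(0.975; 2n−2)) = 0.80, where T is noncentral t with 2n−2 degrees of freedom and noncentrality d√(n/2). For d = 0.81 this gives n = 24.9, so 25 per group, with power 80.1%. The SAP's figure reproduces.

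**Step 3. Completers.** The SAP enrols 30 per arm and allows 20% withdrawal: 30 × (1 − 0.20) = 24 per arm.

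**Step 4. Effect of an unscorable share u (assumed; the documents give none).** n = 24 × (1 − u), rounded.

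| u | n per arm | Detectable effect, 80% power | Power at 0.81 SD |
|---|---|---|---|
| 0 | 24 | 0.83 SD | 78.4% |
| 20% | 19.2 → 19 | 0.93 SD | 68.1% |
| 30% | 16.8 → 17 | 0.99 SD | 62.9% |
| 50% | 12.0 → 12 | 1.20 SD | 47.5% |

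The share differs by outcome. For gait speed, u counts remote baselines only. For the scan, it counts participants with a remote baseline, a device or both. The 0.81 is the SAP's SMAS-30 effect size and serves here only as a yardstick.

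**Step 5. What can be recovered.** If a share r of the 24 have a remote baseline and an in-person follow-up, a change analysis of gait uses 24 × (1 − r) per arm. An analysis of the follow-up value uses all 24. At r = 20% that is 19 against 24. A participant without a baseline adds less information than one with a baseline, because adjustment cannot reduce that participant's residual variance. The gain in precision is therefore somewhat smaller than the gain in numbers, by an amount that depends on a correlation the documents do not give.

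**The case against.** The strongest reply is that little is at stake. These are secondary outcomes of a 60-patient pilot. The protocol's Data Analysis section says that no power statement is required and plans descriptive statistics and changes. The SAP makes no power claim for gait or body composition, so the table in step 4 contradicts no stated figure. The remote group that later attends may also be very small, since people who could not come once may not come later. All of this stands and limits the weight of the point.

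Part of the gap is already covered. Device carriers keep weight and BMI, and weights are a separate secondary outcome in the SAP. That helps less for remote baselines, where only record weights, as available, are mentioned.

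The remedy can be questioned too. A missing-baseline indicator is safe only if whether the baseline is missing does not depend on the arm. The protocol randomises during baseline completion and does not say whether visit mode is settled first. That objection stands as a condition on the fix.

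Three stronger readings are tempting, and the documents do not support them:

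- A reader might infer that a device also prevents the gait test. The restriction covers the scan only; gait is timed with a stopwatch over 15 feet.
- A reader might infer that the SAP commits to imputing every missing value, scans included. The sentence is conditional, its method is absent, and it stands before the secondary outcomes, so its reach to them is unclear. The defect is undefined method and scope.
- A reader might infer bias between arms. Both arms follow the same remote-baseline and device rules, and nothing in the documents ties either status to allocation. Chance imbalance is possible at this size.

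**Conclusion.** The point holds as a modest, inexpensive improvement. Followed as written, the comparison of changes excludes randomised participants who have a valid follow-up gait value or scan but no baseline. The body-composition result can describe only candidates without an implanted device, and the SAP neither says so nor says whether imputation is meant to reach these values.

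The size is unknown, because the documents give neither the remote-baseline share nor the device share. Under assumed unscorable shares of 20% to 50%, 24 completers per arm become 19 to 12. The loss that can be recovered is confined to participants with a remote baseline and an in-person follow-up; for scans, only those without a device.

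The consequence is lost precision and a narrower population for pilot secondary outcomes. The SMAS-30 analysis and its sample-size calculation are not affected.

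**What to change.** Add to the SAP's secondary outcomes:

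1. Analyse gait speed and scan-derived body composition by ANCOVA on the follow-up value adjusted for baseline, as for SMAS-30. Set a missing baseline to the overall mean and include a missing-baseline indicator, so that participants with a remote baseline and an in-person follow-up are kept.
2. State that the mode of the baseline visit is fixed before allocation is known. Item 1 depends on this.
3. Analyse scan outcomes only in participants without a pacemaker, ICD or AICD, do not impute them for device carriers, and limit the conclusion to that group.
4. Name the imputation method and the outcomes it covers.
5. Report the number scorable per arm for each physical outcome, with reasons.

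The cost is a few lines of text, two flags that study records should already supply (visit mode and implanted device), and slightly more analysis work. The stated population for body composition becomes narrower. No study procedure changes, unless visit mode is at present settled after allocation is known.

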#### Data Analysis

Power analyses and study endpoints are not required for minimal risk research, pilot or feasibility studies.

No statistical information. *If checked, please explain*: This is a pilot study to obtain preliminary data for future NIH grant application.

Power Statement: Not required for a pilot study.

Data Analysis Plan: Descriptive statistics and change in secondary endpoints.

Endpoints

Primary: Acceptability and feasibility of health coaching by thoracic transplant candidates. This will be obtained by looking at completion rate of intervention and qualitative surveys after the intervention is completed.

Secondary: Preliminary efficacy data for power calculation for larger R01 application and multisite study. We will look at change in patient reported outcomes of resilience, quality of life, affect, and self-management ability. We will also look at change in frailty parameters.

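### Randomisation is placed during baseline collection, and neither document requires baseline to be complete before the arm of an unblindable intervention is known

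*Protocol*

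**What the plan says.** On the order of events, the protocol (Study Design and Methods) says: "Participants will be randomized to one of two groups while completing their baseline measures". Baseline consists of questionnaires, grip strength, gait speed, the SPPB and a body composition scan at a research visit, followed by a period of activity monitoring.

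Two parts of baseline can run beyond a single sitting:

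- The activity recording: "Participants will also receive an activity monitor at their baseline visit to be worn for 5-7 days".
- The remote route: "If participants are unable to schedule a research visit, they may be mailed the questionnaires or sent via Redcap (electronically"). These participants also receive the monitor by post.

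The arms are weekly coaching calls added to standard care, and standard care alone. SMAS-30 is one of the questionnaires listed under Study Measures. The SAP's primary variable is end-of-study SMAS-30 adjusted for baseline by ANCOVA. Its secondary outcomes are between-group differences in change, including gait speed, activity levels and several questionnaires.

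The protocol's own primary endpoint, under Data Analysis, is different: "Primary: Acceptability and feasibility of health coaching by thoracic transplant candidates".

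Neither document says when participants or staff learn the allocation, or that baseline must be complete before they do.

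**The concern.** ANCOVA on baseline relies on the covariate being unaffected by allocation. A questionnaire answered, or a week of activity recorded, by someone who already knows their arm no longer meets that condition. A candidate told that a coach will call might rate their self-management differently or move more that week. One told that nothing will change might do the opposite.

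Any such shift enters the results through the baseline term. Part of it, in proportion to the ANCOVA slope, passes into the adjusted SMAS-30 difference. All of it passes into an outcome analysed as a change. A larger sample does not remove it, and a baseline taken after disclosure cannot be retaken. At stake are the SAP's efficacy estimates, which are meant to inform a later R01 application.

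**Working it through.** **The plan's own figure.** The SAP gives 25 per arm, an effect size of 0.81, two-sided 0.05 and a two-group t-test. The noncentral t distribution with 48 degrees of freedom gives 80.1% power, matching the stated 80%. The SD is 8.5/√2 = 6.01, and 0.81 × 6.0 = 4.86, matching the stated 4.9. Nothing here disputes that calculation.

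**Form of the bias.** Let a share s of the coached arm learn the allocation before answering, and let their baseline move by b points on average. The ANCOVA estimate is the difference in end-of-study means minus slope × the difference in baseline means. Its bias is therefore −slope × s × b. For a change score it is −s × b.

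**Slope and residual SD.** In the SAP's equal-variance case, the between-person and within-person SDs are both 6.0.

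- Total variance = 36 + 36 = 72, so the total SD is 8.49 (SAP: 8.5).
- Slope = 36/72 = 0.5. The SAP expects between-person variability to be at least as large as within-person, so 0.5 is the lowest slope its assumption allows.
- Residual SD = √(72 × (1 − 0.5²)) = √54 = 7.35.
- Detectable difference on this SD = 0.81 × 7.35 = 5.95. The SAP's 4.9 rests on SD 6.0 and is not the right comparator for a slope of 0.5.

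**Results.** The shifts b and shares s are assumptions; the documents give neither. Null rejection is from the noncentral t with 25 per arm, two-sided 0.05 and SD 7.35. Bias is shown in absolute value.

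| Share of coached arm affected | Shift of 1 / 2 / 3 points: bias | Null rejection |
|---|---|---|
| All | 0.5 / 1.0 / 1.5 | 5.6% / 7.6% / 10.9% |
| Half | 0.25 / 0.5 / 0.75 | 5.2% / 5.6% / 6.4% |
| A quarter | 0.13 / 0.25 / 0.38 | 5.0% / 5.2% / 5.4% |

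For the whole arm, the biases are 0.5/5.95 = 8%, 1.0/5.95 = 17% and 1.5/5.95 = 25% of the detectable difference.

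**Check by simulation.** In 40,000 runs of the ANCOVA with the whole arm shifted, no shift gave 4.9% rejection. Shifts of +1, +2 and +3 gave mean effects of −0.50, −1.00 and −1.48 and rejection of 5.6%, 7.7% and 10.6%. Shifts of −1, −2 and −3 gave +0.50, +1.00 and +1.49 and rejection of 5.5%, 7.4% and 10.8%. An upward shift in the coached arm therefore works against coaching, and a downward shift in its favour.

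**Which measures are exposed.**

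- *Activity recording:* it begins at the visit and lasts 5-7 days, so it continues after an allocation made at that visit.
- *Home questionnaires, including SMAS-30:* they can be completed after allocation. The share of participants using this route is not given.
- *Physical tests and questionnaires done at the visit:* exposed only if the arm is revealed during the visit. Remote participants are sent only questionnaires and a monitor.

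**The case against.** The strongest reply is that being randomised is not the same as being told. The sentence is compatible with staff generating the assignment in the background and withholding it until baseline is finished. The usual route is a visit, and the remote route is a fallback. The shift sizes have no source in the documents, and the table shows little effect unless most of the arm is affected by 2-3 points. The study is a pilot whose protocol endpoint is feasibility. Follow-up SMAS-30 will be self-reported by unblinded participants whatever is done at baseline.

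Much of this stands, and it limits the weight of the point. It does not remove it. The protocol states an order of operations that permits disclosure before baseline ends, and nothing elsewhere prevents it. The SAP names SMAS-30 as its primary variable with a significance threshold, and both documents intend the results for R01 planning. Unblinded follow-up is a separate source of bias and no reason to leave this one open.

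A reader might also infer that follow-up is timed differently in the two arms. The protocol says of controls "Participants in one group will continue to receive the standard pre-transplant care for 12 weeks" and of coaching calls "with the goal of finishing 12 calls over a 16-week period". But Study Measures places the second assessment "at baseline and after completing the intervention (or in an equivalent time-frame if a control patient"), so comparable timing is already intended and only its definition is missing. That does not support a bias claim. At most, the three passages should be reconciled.

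**Conclusion.** The point holds as an avoidable risk of bias that should be closed. It is more than missing detail, because the stated sequence is itself the weakness.

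Its size is unknown. Under the equal-variance model with a slope of 0.5, 25 per arm and assumed shifts of 1-3 points across the whole coached arm, the bias is 0.5-1.5 points and null rejection 5.6-10.9%. With a quarter of the arm affected it is negligible. The sign could go either way.

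Three stronger readings are tempting, and the documents do not support them:

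- *That baseline is in fact biased, or that the error rate is 10.9%.* The documents do not say when the arm is disclosed or how many participants are remote, and they give no size of shift. The 10.9% is the most extreme case illustrated.
- *That all baseline measures are equally exposed.* Those finished in one visit are exposed only if the arm is revealed there.
- *That the trial's main conclusion is at risk.* Acceptability and feasibility, judged by completion rate and post-intervention surveys, do not use the baseline measures.

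**What to change.** Replace the sentence on randomisation in Study Design and Methods with:

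> Participants will be randomised, and the allocation disclosed, only after the baseline questionnaires are completed (or received, if remote), any baseline physical tests are done, and the baseline activity-monitor wear period has ended; dates of baseline completion and disclosure will be recorded.

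The calculated power, significance level and planned numbers stay as they are: 25 evaluable and 30 enrolled per arm. Bias from a post-disclosure baseline shift is removed by design, and the recorded dates let a reader verify it.

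The cost is about one week's delay before allocation, plus postal time for remote participants. A few candidates may be transplanted in that interval. Because randomisation and disclosure both follow baseline, those losses fall before randomisation and do not draw on the SAP's 20% withdrawal allowance or the completion rate. Withholding only the disclosure, after randomising at the visit, would put those losses after randomisation.
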